1. PROJECT TITLE

Ovarian Morphology and Theca Cell Androgen Production in Women with Polycystic Ovary Syndrome (PCOS)

3. FACILITIES

Clinical and Translational Research Institute and UCSD/Reproductive Partners Medical Group

4. ESTIMATED DURATION OF THE STUDY

2 years

5. LAY LANGUAGE SUMMARY OR SYNOPSIS (no more than one paragraph)

Women with PCOS suffer from excess male hormone (androgen) production by the ovary. Androgen is made by cells that surround follicles that contain eggs. As the follicles (and eggs) grow and mature, there are more androgen producing cells. Women with PCOS have more follicles than normal women and therefore more androgen producing cells. While androgen production has been associated with the number of follicles, the relationship to the individual size of follicles in PCOS or normal women. This study intends to determine whether the size and number of ovarian follicles are correlated to androgen production in PCOS and normal women.

6. SPECIFIC AIMS

Specific Aim: To determine the relationship between ovarian follicle size and ovarian androgen production in women with PCOS and normal women

Hypothesis: In PCOS excess androgen production is positively correlated to ovarian follicle size

7. BACKGROUND AND SIGNIFICANCE

In women with polycystic ovary syndrome (PCOS), the major abnormality is excessive ovarian androgen production marked by increased serum testosterone (T) and androstenedione (A) levels. Studies to determine the alteration in ovarian steroidogenesis that lead to abnormal production of ovarian androgens have revealed increased CYP17 gene expression with accentuated 17-hydroxylase activity leading to exaggerated 17-hydroxyprogesterone (17P) responses to LH stimulation. In contrast, T and A responses did not distinguish between PCOS and normal women, although these androgens were clearly greater in the former compared to the latter group. As a result, 17P responsiveness has been employed to determine the functional capacity of the ovary to produce androgen. Stimulatory agents have included GnRH agonist, Lupron, at a dose of 10 microgram per kilogram, or hCG at a dose of 10,000 IU.

We recently showed that hCG administered intravenously in a dose-response fashion revealed gradual increases of 17P and a non-dose dependent increase of serum T and A. The pattern of steroid hormone production revealed the predominant pathway by which androgens are generated in women with PCOS. Extending these studies, we selected the mid-maximal dose of hCG to stimulate ovarian androgens and included morphometric measures of the ovary, such as ovarian follicle number (as determined by ultrasound) and related hormones, such as anti-mullerian hormone and inhibin B, both products of the ovarian follicle. The results showed that increased androgen and 17P responses in PCOS women were associated with increased antral follicle number and greater AMH levels compared to normal women. Inhibin B levels were similar between groups.

Based on responses observed in normal women, the PCOS women were divided into two groups. Those with 17P responses that did not exceed the normal mean plus 2 standard deviations (normal responder PCOS; NR-PCOS) and those that did exceed the normal response (high responder PCOS; HR-PCOS). This separation occurred at a rate of 50%. Notably, serum AMH levels were 2-fold higher in NR-PCOS compared to HR-PCOS. This finding was puzzling as serum AMH levels have been shown to correlate to the number of small follicles present in ovaries suggesting that AMH may be a surrogate for small follicle number. However, both PCOS subgroups had equivalent follicle numbers. We hypothesize that the NR-PCOS have greater number of small follicles compared to HR-PCOS. To address this issue we propose to assess the number of small follicles in NR- and HR-PCOS women and normal controls.

In a secondary consideration the HR-PCOS group was heavier than the NR-PCOS. This implies that the HR-PCOS women may have had greater insulin resistance and hyperinsulinemia that may have contributed to the significantly higher 17P responses to hCG. As a result, we will also perform an oral glucose tolerance test in all subjects.

Power Analysis

Results of our pilot study have shown that approximately 50% of PCOS women will exhibit 17OHP responses to hCG stimulation similar to those of normal women. Consequently, a sample size of 20 subjects in each group has an 80% power to detect a difference in the means of 0.820 ng/ml (the difference between the average 17OHP expression level in high responder PCOS women (HR-PCOS), 2.840 ng/ml, and that of normal responder PCOS (NR-PCOS) women, 2.02 ng/ml), which is a 33% increase. In the proposed study, we believe that HR-PCOS (n=20) will show significantly greater (33% more) 17OHP production in response to hCG stimulation than NR-PCOS (n=20) at a power of 0.8 and a type I error rate of 0.05. We will recruit 25 subjects in each group to allow for subject drop out. A secondary analysis will be performed between women with PCOS and normal controls (n=20).

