9. RESEARCH DESIGN AND METHODS

Screening

40 women with PCOS and 20 normal women will be studied. Patients will be recruited from reproductive medicine clinics at UCSD or from the community by means of advertisement. Subjects will have a screening visit to establish eligibility and to sign the informed consent. They will have a history and physical examination performed which will include a urine pregnancy test, thyroid studies, a fasting chemistry panel, and a hemoglobin. If the hemoglobin is less than 11 gm/dL, the subject will be given ferrous sulfate pills and will return at another date when her hemoglobin is above 11 gm/dL.

Protocol

1. Subjects will have a urine pregnancy test at UCSD/Reproductive Partners Medical Group. Images of the both ovaries will be obtained using vaginal ultrasound and the number, size, and spatial arrangement of ovarian follicles will be noted for both ovaries in each subject. The ultrasound will be completed for each subject according to schedule availability and each subject shall maintain normal activity before and after the imaging study.
2. Normal subjects will be admitted to the CTRI during the mid follicular phase (Days 5-9) while PCOS women will be anovulatory and will not have a cycle day parameter. A urine pregnancy test will be done on admission.
3. On study day one, recombinant-hCG (r-hCG) will be administered intravenously at a dose of 25

micrograms.

4. Blood samples will be obtained at T = -0.5, 0, and +24 hours.
5. Blood sample will be used for DNA testing to identify genes that may be associated with androgen production.
6. Sera will be assayed at all time points for steroid and peptide hormones including AMH, inhibin B, insulin, 17OHP, androstenedione, testosterone, dehydroepiandrosterone, estradiol, progesterone, LH, and FSH.
7. One to two weeks after hCG stimulation testing each subject will come to the CTRI for an Oral Glucose Tolerance Test (OGTT). Each subject will ingest 75 gm of a glucose solution and blood samples will be obtained at 0, 15, 30, 60, 120 and 180 minutes after the glucose load.
8. Subjects will be advised to follow a 150gram carbohydrate diet for 3 days prior to OGTT

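### The correlation hypothesis has no matching analysis: the only within-PCOS follicle comparison described splits the continuous 17OHP response into two classes, which costs power if the relation is linear

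*Combined protocol and SAP*

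**What the plan says.** Section 6 (Specific Aims) gives the one formal hypothesis, and it is about a continuous relation: "In PCOS excess androgen production is positively correlated to ovarian follicle size".

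Section 7 (Background and Significance) puts the follicle question in classes. In the pilot, "Based on responses observed in normal women, the PCOS women were divided into two groups", with the lower class defined as "Those with 17P responses that did not exceed the normal mean plus 2 standard deviations (normal responder PCOS; NR-PCOS". Half of the pilot's PCOS women fell on each side. The section then states a hypothesis about those classes, "We hypothesize that the NR-PCOS have greater number of small follicles compared to HR-PCOS", and the plan that follows from it: "To address this issue we propose to assess the number of small follicles in NR- and HR-PCOS women and normal controls". The Power Analysis in the same section also compares HR (n=20) with NR (n=20), on 17OHP and not on any follicle measure.

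Section 9 (Research Design and Methods) fixes the size: "40 women with PCOS and 20 normal women will be studied". Every subject has follicle number and size recorded by ultrasound, and has 17OHP and AMH assayed at -0.5, 0 and +24 hours. No statistical test is named for either follicle question. Nothing says whether the NR/HR cut-off will be the pilot's value or a new one.

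**The concern.** The stated hypothesis and the described comparison do not meet. The hypothesis relates androgen production to follicle size on a continuous scale. The comparison relates small-follicle number to a two-level version of the 17OHP response, which Section 7 uses as its measure of the ovary's capacity to make androgen. Dichotomising treats a woman just under the line as the opposite of one just over it, and as identical to one far below it.

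Two things are at stake. With only 40 PCOS women, power lost to the split is hard to spare. And while no analysis of the Section 6 hypothesis is written down, the choice between a continuous and a grouped analysis can be made after the data are seen.

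**Working it through.** **The plan's own figure.** Section 7 states 80% power with 20 per group for a 17OHP difference of 0.820 ng/ml (2.840 against 2.02) at type I error 0.05. No SD is given, so it can only be solved backwards. Two-sided, normal approximation: SD = 0.820 / [(1.960 + 0.842) × √(2/20)] = 0.820 / 0.886 = 0.93 ng/ml. The figure concerns 17OHP, so it says nothing about power for follicles.

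**Inputs.** From the documents: 40 PCOS women, 20 controls, a 50:50 split in the pilot, cut at normal mean + 2 SD. Assumed: bivariate normal response and follicle measure, linear relation, two-sided 0.05, true correlation r between 0.30 and 0.50.

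**Information kept by a split.** For a normal variable cut so that a fraction p lies on one side, the share kept is φ(z_p)² / [p(1 − p)].
- p = 0.5: 2/π = 0.637, a loss of 36%. Forty women count as 40 × 0.637 = 25.5.
- To match 40 women analysed continuously, a split analysis needs 40 / 0.637 = 63.
- Uneven splits lose more: 38% at 40:60, 42% at 30:70, 51% at 20:80.

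**Power at n = 40** (20,000 simulated studies per row; 50:50 split at the true median).

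| True r | Continuous | Split |
|---|---|---|
| 0.30 | 47% | 32% |
| 0.40 | 74% | 54% |
| 0.43 | 81% | 60% |
| 0.50 | 92% | 76% |

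Hand check at r = 0.43 with Fisher's z:
- Continuous: atanh(0.43) × √37 = 0.460 × 6.083 = 2.80; 2.80 − 1.96 = 0.84, power about 80%.
- Split: r shrinks to 0.43 × √0.637 = 0.343; atanh(0.343) × 6.083 = 2.18; 2.18 − 1.96 = 0.22, power about 59%.

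The value 0.43 is chosen because it is the correlation detectable with 80% power at n = 40: tanh(2.802 / √37) = 0.43. After the split the detectable value is about tanh(2.802 / √22.5) = 0.53.

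**If the relation is a step instead.** With a true 0.9 SD jump in the follicle measure at the cut and n = 40, simulated power is 57% continuous and 78% split.

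**The cut-off, if it were re-estimated from the 20 new controls.** SE of mean + 2 SD = √[1/20 + 4/(2 × 19)] = √(0.050 + 0.105) = 0.39 control SD. The nominal 2 SD line would then fall between about 1.2 and 2.8 control SD in 95% of studies. If PCOS responses centre on the line with an SD of one to two control SDs (assumed; the documents give no SD), the HR count among 40 women would range over about 8–32 to 12–29. Much of that is ordinary sampling: a fixed 50% line already gives 20 ± 1.96 × √(40 × 0.5 × 0.5), about 14–26. The effect on power is small: at r = 0.43 it falls from 60% to 57–59%.

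**The case against.** The strongest reply is that the plan does not choose a dichotomised test. Sections 5 and 6 declare a correlation objective, Section 9 collects the data for it, and the NR/HR comparison serves a narrower puzzle in Section 7: why AMH was twice as high in NR-PCOS when follicle numbers were equivalent. This stands in part. A reader might infer that the plan tests its whole follicle question by splitting. The documents support that only for the small-follicle hypothesis; for the correlation hypothesis they name no analysis at all. That silence is the gap.

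Second, the mean + 2 SD rule is past-tense description of the pilot. Its reuse is a fair inference, since the labels and the 50% rate are carried into the new sample size and no other definition appears, but it is not a written rule. A reader might go further and infer that 20 controls will fix the line. No sentence says so: Section 7 names the controls for the follicle comparison and a secondary PCOS-versus-normal analysis. The pilot's line may be carried over, and the number of pilot controls is not given.

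Third, the loss from splitting depends on the shape of the relation. Section 7 speaks of two responder types. If follicle number really steps between them, the split is the more powerful analysis, as the 78% against 57% above shows. The documents establish neither shape. For the same reason they do not support reducing NR/HR to description only: it carries a stated hypothesis and is the comparison that the sample size was built on.

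**Conclusion.** The point holds as a mismatch between hypothesis and analysis, with a better analysis available from data already collected. Under a normal response, a linear relation and the pilot's 50:50 split, grouping discards about 36% of the information and costs 15 to 21 percentage points of power for r between 0.30 and 0.50 (47 − 32 = 15; 81 − 60 = 21; 92 − 76 = 16). These are conditional figures, r is assumed, and a true step at the cut reverses the ranking.

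The cut-off is a secondary matter. Its source is unstated. If it were re-estimated from 20 controls, group membership could shift noticeably between repeats of the study, but power would barely change.

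**What to change.** In Section 7, state that within PCOS, follicle size and small-follicle number (and AMH) will be related to the continuous 17OHP response at +24 h by regression or rank correlation, with a 95% confidence interval, as the main analysis of the Section 6 hypothesis. Rank correlation serves if the response is skewed. Keep NR versus HR as a supporting analysis of the Section 7 small-follicle hypothesis, which also covers the possibility of a step.

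State before analysis which cut-off defines NR and HR: the pilot's value, or one derived from this study's controls by a written rule.

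The cost is slightly more analysis work and one more prespecified test. No added subjects, visits or assays are needed.

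### The power statement twice calls its 0.820 ng/ml difference 33%; on its own means, with NR-PCOS as the base it names, the increase is 41%

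*Combined protocol and SAP*

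**What the plan says.** The only sample-size justification is the Power Analysis paragraph in section 7 (Background and Significance). It states that "a sample size of 20 subjects in each group has an 80% power to detect a difference in the means of 0.820 ng/ml". The HR-PCOS mean behind that difference is printed as 2.840 ng/ml. For the comparator the text reads: "that of normal responder PCOS (NR-PCOS) women, 2.02 ng/ml), which is a 33% increase".

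The next sentence restates the target in relative terms only: "HR-PCOS (n=20) will show significantly greater (33% more) 17OHP production in response to hCG stimulation than NR-PCOS (n=20". It gives neither the means nor the absolute difference, and it is the sentence that sets the design's error rates, with the effect taken to be detectable "at a power of 0.8 and a type I error rate of 0.05".

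The paragraph gives no standard deviation, test or sidedness. It names no base for the percentage other than NR-PCOS.

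**The concern.** The two printed means and the printed percentage cannot all be right. An increase of HR-PCOS over NR-PCOS takes the NR-PCOS mean as its denominator, and on that base the stated difference is well above 33%.

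The percentage matters because of where it is repeated. In the second sentence it is the only expression of the effect, and it stands beside the power and the type I error rate. A reader who relies on that sentence takes the study to have 80% power for a smaller relative difference than the one to which the 80% is attached. The slip therefore makes the study look more sensitive than the paragraph supports.

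**Working it through.** **Inputs**, all from the Power Analysis in section 7: HR-PCOS mean 2.840 ng/ml; NR-PCOS mean 2.02 ng/ml; difference 0.820 ng/ml; stated increase 33%; 20 per group; power 0.8; type I error 0.05.

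**1. The absolute difference reproduces.** 2.840 − 2.02 = 0.820 ng/ml, as stated.

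**2. The percentage does not.** Increase over NR-PCOS = (HR mean − NR mean) / NR mean = 0.820 / 2.02 = 0.406, or 41%. The stated 33% is 7.6 percentage points lower.

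**3. Rounding of the means does not explain it.** Taking each mean to the edge of its printed precision:
- lowest: (2.8395 − 2.025) / 2.025 = 40.2%
- highest: (2.8405 − 2.015) / 2.015 = 41.0%

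**4. Other ways of forming the percentage.**

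| Calculation | Result |
|---|---|
| HR-PCOS mean as base: 0.820 / 2.840 | 28.9% |
| Midpoint of the two means as base: 0.820 / 2.43 | 33.7% (rounds to 34%) |
| Log ratio: ln(2.840 / 2.02) | 34.1% |

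None of these rounds to 33%, and none is an increase over NR-PCOS.

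**5. What 33% over NR-PCOS would mean.** 0.33 × 2.02 = 0.667 ng/ml, which puts the HR-PCOS mean at 2.02 × 1.33 = 2.69 ng/ml. The shortfall against the stated difference is 0.820 − 0.667 = 0.153 ng/ml, and 0.153 / 0.820 = 19%.

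**6. How far apart the two readings are (illustration only).** No SD is given, so the 80% cannot be verified. Assume that the 80% at 0.820 ng/ml is correct, with 20 per group and alpha 0.05 two-sided. By the normal approximation the implied common SD is 0.820 / [(1.960 + 0.842) × √(2/20)] = 0.93 ng/ml; with a t-test it is 0.90. On that SD, power for 0.667 ng/ml with 20 per group is about 62%, and 80% power would need 30 (t) to 31 (normal) per group. If alpha is one-sided, the implied SD is 1.02 to 1.04 and the power about 65%, again with 30 to 31 per group. The SD here is derived from the power claim itself, so these figures are no evidence about the study's real power. They show only that 33% and 0.820 ng/ml are not interchangeable targets.

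**The case against.** The strongest reply is that this is a labelling slip. The first sentence ties the 80% to the absolute difference, both means are printed beside it, and they subtract correctly. Nothing shows that 33% entered the calculation. Later sections carry forward only the headcounts of 40 PCOS and 20 normal women, not the percentage. The midpoint base is also a plausible origin for the figure: with the roughly 50:50 split of PCOS women it approximates the overall PCOS mean, and 33.7% becomes 33% if truncated.

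Much of this stands. The target of 0.820 ng/ml is internally consistent, and the sample size is not shown to be wrong. The midpoint may well be where the number came from. It does not rescue the wording, because the text describes an increase over NR-PCOS and names that group as the comparator. Nor is the percentage only a gloss on figures beside it: the second sentence gives it alone, next to the power and type I error. The missing SD, test and sidedness are a separate reporting gap and are not part of the error.

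**Conclusion.** The concern holds. On the plan's own means and named base the increase is 41% (40.2% to 41.0% allowing for rounding), and 33% is wrong in both places. In absolute terms the label understates the stated target by 0.153 ng/ml, or 19%.

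This assumes that the two printed means are right. The documents cannot confirm that, although the means agree with the printed difference. No conclusion is drawn about the study's true power. The correction is worth making because the error sits in the plan's only power statement and favours the study, but it is not shown to change the number of women needed.

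**What to change.** 1. Check 2.840 and 2.02 ng/ml against the pilot data before editing anything.
2. If both stand, change 33% to 41% in both sentences, and tie the 80% power to 0.820 ng/ml (41%) only.
3. If either mean is wrong, correct it together with the difference and the percentage, and rerun the power calculation.
4. In the same edit it would help to state the pilot within-group SD, the test and the sidedness used, so that the 80% can be checked.

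The cost is a look-up of two means and two changed percentages in one paragraph. If the means stand, the target difference, sample size and study procedures are unchanged. Only if a mean proves wrong could the sample size need to be reconsidered.

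### The only powered comparison is of 17OHP between groups apparently formed on 17OHP; the follicle-size aim has no power figure, size summary or named androgen measure

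*Combined protocol and SAP*

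**What the plan says.** Section 6 (Specific Aims) has one aim: to relate ovarian follicle size to ovarian androgen production in women with PCOS and normal women. The hypothesis is a positive correlation in PCOS.

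Section 7 describes how the pilot divided its PCOS women. Normal responders were "Those with 17P responses that did not exceed the normal mean plus 2 standard deviations (normal responder PCOS; NR-PCOS"; the rest were high responders (HR-PCOS). The section expands 17P as 17-hydroxyprogesterone, which is 17OHP. It goes on to a follicle hypothesis, "We hypothesize that the NR-PCOS have greater number of small follicles compared to HR-PCOS", having noted that in the pilot "both PCOS subgroups had equivalent follicle numbers".

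The Power Analysis in section 7 starts from the pilot finding that "approximately 50% of PCOS women will exhibit 17OHP responses to hCG stimulation similar to those of normal women" and moves directly to 20 women per group. It gives 80% power and a 0.05 error rate for a difference of 0.820 ng/ml (2.840 against 2.02) and concludes: "we believe that HR-PCOS (n=20) will show significantly greater (33% more) 17OHP production in response to hCG stimulation than NR-PCOS (n=20". On recruitment: "We will recruit 25 subjects in each group to allow for subject drop out". Sections 9 and 10 say that 40 women with PCOS and 20 normal women will be studied.

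Section 9 describes one r-hCG test, with blood drawn at -0.5, 0 and +24 hours. Number, size and arrangement of follicles are recorded in both ovaries. 17OHP, testosterone, androstenedione and dehydroepiandrosterone are among the hormones assayed.

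**The concern.** There are two linked problems.

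First, if women are again labelled HR or NR by their 17OHP response, a later comparison of 17OHP response between the labels mostly reports the effect of labelling. The groups will differ whether or not two kinds of PCOS exist. A significant result could then be read as support for distinct subgroups when the cut-off alone would produce it.

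Second, that comparison is the whole justification for the sample size, and it does not bear on the aim. A reader sees 80% power and may take it to apply to the follicle-androgen relation. Nothing in the plan says what strength of association 40 PCOS women can detect. Nor does it say which follicle summary and which androgen will be correlated. With several androgens and many possible follicle summaries available, that choice stays open until after the data are seen.

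**Working it through.** **1. The plan's own figure.** Inputs from section 7: difference 0.82 ng/ml, 20 per group, power 0.80, alpha 0.05 (two-sided assumed; sidedness is not stated). No SD is given, so 20 cannot be reproduced directly. With n = 2(1.960 + 0.842)² SD² / 0.82², setting n = 20 gives SD = 0.82 × √10 / 2.802 = 0.93 ng/ml; the t-test version gives 0.90. The stated power therefore implies a gap of 0.82/0.90 = 0.91 SD. At assumed SDs of 0.75, 1.0 and 1.25 the formula gives 14, 24 and 37 per group.

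**2. Does the pilot rule carry over?** The power paragraph keeps the pilot's labels and its 50% rate and derives 20 per group from them. No other grouping rule appears, and there is only one hCG test. Reuse is strongly implied but not stated. The document also does not say whether the grouping measure and the compared measure are the same; the sampling times would allow, for example, a rise for one and a +24 h level for the other.

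**3. What the split alone produces.** Model: 40 women from one normal population, cut at its median (the pilot split fell at 50%), t-test at 0.05, 20,000 replicates. If the grouping and compared measures correlate ρ, the true gap is ρ × 2√(2/π) = 1.596ρ population SDs.

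| Correlation | True gap (SD) | Samples with p<0.05 |
|---|---|---|
| same measure | 1.60 | 100% |
| 0.7 | 1.12 | 99% |
| 0.5 | 0.80 | 75% |
| 0.3 | 0.48 | 32% |
| 0.2 | 0.32 | 17% |
| 0 | 0 | 5% |

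For the same measure with skewed distributions (lognormal, exponential) the rate was 99.4% to 100%. The documents do not give the correlation, so they do not settle which row applies.

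**4. The aim.** For a correlation by Fisher's z, two-sided 0.05:
- Detectable |r| at 80% power with n = 40: tanh(2.802/√37) = tanh(0.461) = 0.43.
- Power at r = 0.3: Φ(0.3095 × √37 − 1.960) = Φ(−0.077) = 47%.
- Women needed for 80% power at r = 0.3: (2.802/0.3095)² + 3, rounded up to 85.
- Adjusted for one covariate, n = 40: tanh(2.802/√36) = 0.44.
- Within 20 normal women: tanh(2.802/√17) = 0.59.

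**5. Small-follicle count, HR against NR.** The detectable difference (noncentral t, 80% power) is 0.91 SD at 20/20 and 0.94 SD at 15/25. With 40 women and a 50% rate, exactly 20/20 occurs with probability C(40,20)/2⁴⁰ = 12.5%, and 15/25 or closer with probability 92%.

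**6. Numbers recruited and studied.** 25 recruited for 20 is a 20% allowance. Two PCOS groups of 25 make 50, and 50 × 0.80 = 40, which agrees with the 40 in sections 9 and 10 if that means completers. The protocol does not say so.

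**The case against.** The strongest reply is that nothing is statistically invalid. A reader might infer from the table that the type I error of the HR-NR comparison is really about 100%. That does not follow. The plan claims only that HR-PCOS will have higher 17OHP than NR-PCOS. Splitting on the same or a correlated measure makes the group means truly different, so the rejections are correct; where the true gap is zero, the test rejects 5% of the time. This part of the reply stands. What remains is that the result is uninformative, because the split supplies the gap.

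It can also be said that the grouping rule is described only for the pilot, and that the implied 0.91 SD fits a between-measure correlation near 0.5 better than the same-measure case. At 0.5 the gap in within-group SDs is 0.80/√(1 − 0.25 × 0.637) = 0.87, against 1.6 to 2.7 for the same measure across the distributions tried. Both are fair reasons to keep this half conditional. However, the 0.91 is back-solved from the power claim and does not show which case holds.

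Finally, the follicle side is not blank: section 6 names a positive correlation and section 7 names a count of small follicles. That is true, and a reader should not infer that no analysis is indicated. What is missing is a named test, a per-woman size summary, a size limit for small, a named androgen measure and a power figure.

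**Conclusion.** The point holds in two parts, with different certainty.

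Unconditionally, the only sample-size rationale concerns a comparison that does not address the stated aim. For the aim, 40 PCOS women give 80% power only at |r| of 0.43 or more, and 47% at 0.3. This assumes 40 women with complete data, a two-sided 0.05 test and Fisher's z. It refers to the correlation between measured values. Ultrasound is scheduled by availability rather than tied to the hCG test, so the underlying association may need to be stronger.

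Conditionally, if the pilot rule is reused, a 17OHP difference between HR and NR is built in: certain if one measure does both jobs, otherwise in proportion to the correlation. The simulated rates assume one population and a cut at its median. They do not show an inflated error rate, and they do not show that the subgroups are unreal.

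A reader might also apply the 20% allowance to the 40 and conclude that only 32 would complete. The documents do not support that, since 50 recruited and 40 studied is a consistent reading and the allowance would be counted twice.

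This should be corrected before analysis, because the stated power is not power for the study's question.

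**What to change.** Revise section 7 as follows.

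1. State the HR/NR rule for this study. Report the HR-NR difference in 17OHP as descriptive, and delete its power, type I error and significance claim.
2. Make the main analysis the correlation, within PCOS women, of one follicle-size summary with one androgen measure, both chosen by the sponsor before the data are seen. Mean follicle size over both ovaries and the 17OHP response are one example; section 7 notes that "17P responsiveness has been employed to determine the functional capacity of the ovary to produce androgen". Report the same correlation in the normal women as secondary, since the aim includes them. Because "In a secondary consideration the HR-PCOS group was heavier than the NR-PCOS", add a BMI-adjusted sensitivity analysis in PCOS.
3. Replace the power statement with: With 40 PCOS women completing ultrasound and hCG testing, the study has 80% power at two-sided 0.05 to detect |r| of 0.43 or more (47% power if r = 0.3). This is a detectable, not an expected, effect.
4. Say whether the 40 PCOS women in sections 9 and 10 are the completers from the 25 per group recruited in section 7.
5. Keep small-follicle count, HR against NR, as a secondary comparison, with a stated size cut-off and its detectable difference (about 0.91 SD at 20/20). If the main analysis uses the 17OHP response, say that the two overlap. With no association, their test statistics correlated 0.81 in simulation when both used the same follicle measure, and 0.41 when the two follicle measures correlated 0.5.

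The cost is rewording the power section and adding one analysis paragraph. Follicle size and 17OHP are already collected, and BMI is needed for eligibility, so no procedures are added. No subjects are added if 0.43 is accepted as the detectable correlation; aiming for 0.3 would need about 85 PCOS women. The stated power becomes less favourable.
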